## 17 Cohort-specific information

This section contains details that pertain to specific cohorts and treatment arms and should be considered as supplementary to information presented in the preceding core protocol sections and respective Investigator's Brochures. If there are no cohort- or treatment-specific details presented for a given topic (e.g., cohort- or treatment-specific eligibility criteria, study restrictions, dose adjustment rules), then the information in the corresponding section in the core protocol for that topic should be implemented without further adjustment.

### 17.1 Cohort 1

Cohort 1 will evaluate the use of LYS006 alone and tropifexor (LJN452) in combination with LYS006 for the treatment of elevated liver fat, liver inflammation and liver fibrosis in NAFLD participants who manifest a NASH-like biomarker phenotype. The drug combination of LYS006 and tropifexor (LJN452) may provide clinical benefit beyond that of either drug alone, considering different, complementary mechanisms of action of these drugs.

Approximately 50 participants will be randomized in a 1:1 ratio to one of the following treatment arms:

- Arm 1: LYS006 Commercially Confidential Information
- Arm 2: Tropifexor (LJN452) Commercially Confidential Information + LYS006 CCI

#### 17.1.1 Cohort 1, Arm 1: LYS006

##### 17.1.1.1 Introduction

This treatment arm will evaluate LYS006 alone.

Commercially Confidential Information

#### **17.1.1.3 Rationale for the single treatment**

The LYS006 CCI single treatment arm will allow assessment of LYS006 safety, tolerability and efficacy and comparison of data to LYS006 combination in order to determine whether the single agent effects are additive, synergistic or antagonistic.

Commercially Confidential Information

---

Commercially Confidential Information

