Secondary Objectives	
 
• Objectives 1-4: To determine the effect of twelve weeks of single or combination therapy on 
 
• 1: Circulating markers of ongoing liver fibrosis as measured by the Enhanced Liver Fibrosis (ELF) Test
 
• 2: Intrahepatic lipid content (percent liver fat) by measuring Magnetic Resonance Imaging-Proton Density Fat Fraction (MRI-PDFF)
 
• 3: Cardiometabolic risk parameters by measuring body weight, waist and hip circumference, waist-to-hip ratio, Homeostasis Model Assessment of Insulin Resistance (HOMA-IR), hemoglobin A1C (HbA1c), fasting glucose, fasting insulin, and fasting lipid profile
 
• 4: Circulating markers of liver and/or systemic inflammation by measuring liver function tests (ALT) and high-sensitivity C-reactive Protein (hsCRP)
 
 
 
 
And
 
 
• Objective 5: To evaluate the PK of each individual agent when administered as a single or combination therapy by collecting and analyzing blood samples to obtain plasma concentrations over 12 weeks of treatment.
 

Study design	
This is a non-confirmatory, multicenter, open label, platform study in NAFLD patients with a NASH-like biomarker phenotype to examine the effects of single and combination therapies over 12 weeks of treatment.
 
Commercially Confidential Information

	
Each cohort consists of a 33-day screening period, 27-day baseline period, 12-week treatment period, and a study completion visit (End of Study [EOS] 1) approximately 28 days after the last drug administration. For drugs with longer half-lives, the same study design will be followed, however, an additional post-treatment follow-up visit (EOS2) will occur 56 days after the last drug administration, and study completion evaluations will take place at this visit instead.

Population	
The study population will be comprised of adult (18 years or older) male and female NAFLD patients with a NASH-like biomarker phenotype.
 
Approximately 25 participants per arm will be enrolled in the study and 20 per arm are expected to be evaluable. Cohort 1 consists of two treatment arms. Multiple arms/cohorts are planned and future therapies will be introduced in subsequent protocol amendments.

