## **4.3 Rationale for choice of control drugs (comparator/placebo) or combination drugs**

There is currently no appropriate comparator for use in the NASH/NAFLD patients.

Commercially Confidential Information

---

Commercially Confidential Information

While the primary purpose of NEXSCOT is to detect high efficacy drug combinations, single drug treatment arms may also be studied in those situations where the efficacy of the particular drug on the relevant endpoint biomarkers in the relevant patient population has not been previously measured. In this case, the treatment effects of the single drug treatment arm would be compared to both the combination drug effects and the historical placebo effects.

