## **12 Data analysis and statistical methods**

Any data analysis carried out independently by the investigator should be submitted to Novartis before publication or presentation.

All data will be listed, summarized and analyzed by cohort and treatment. Combined cohort analysis will be performed as appropriate.

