### **17.1.2 Cohort 1, Arm 2: LYS006 and tropifexor**

#### **17.1.2.1 Introduction**

This treatment arm will evaluate a free combination of LYS006 and tropifexor.

Commercially Confidential Information

Commercially Confidential Information

---

[figure not shown]
Commercially Confidential Information

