### **Tropifexor human efficacy in NASH**

Preliminary data from the ongoing Novartis CLJN452A2202 study in patients with NASH provides evidence that tropifexor 90 µg daily for 12 weeks improved liver fat and ALT versus placebo. 140 µg and 200 µg daily doses of tropifexor are under evaluation in this study at the present time.

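### Cohort 1 can estimate what tropifexor adds to LYS006, but its two arms cannot by themselves classify the drugs' joint effect as additive, synergistic or antagonistic

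*Protocol*

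**What the plan says.** Protocol 17.1.1.3 says the LYS006 arm permits assessment of that drug and a "comparison of data to LYS006 combination in order to determine whether the single agent effects are additive, synergistic or antagonistic".

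The arm structure is readable and consistent. The protocol summary states "Cohort 1 consists of two treatment arms". Protocol 17.1 adds "Approximately 50 participants will be randomized in a 1:1 ratio to one of the following treatment arms", and SAP 4.1.1 repeats this. For Arm 1, "This treatment arm will evaluate LYS006 alone" (17.1.1.1). For Arm 2, "This treatment arm will evaluate a free combination of LYS006 and tropifexor" (17.1.2.1). Cohort 1 has no tropifexor-alone arm and no placebo arm.

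Three other places bear on the point:

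- Protocol 4.3 reserves single-drug arms for drugs whose efficacy on the relevant biomarkers has not yet been measured in the relevant population. In that case "the treatment effects of the single drug treatment arm would be compared to both the combination drug effects and the historical placebo effects".
- The Arm 2 section on tropifexor efficacy in NASH cites preliminary data from a separate ongoing study, in which tropifexor "daily for 12 weeks improved liver fat and ALT versus placebo".
- Protocol 12 says "Combined cohort analysis will be performed as appropriate", and later cohorts may be added by amendment.

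**The concern.** Classifying a joint effect as additive, synergistic or antagonistic means comparing what tropifexor does on top of LYS006 with what it does on its own. Cohort 1 observes only the first. As written, 17.1.1.3 attributes to the LYS006-versus-combination comparison an answer that this comparison cannot give alone.

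What is at stake is how the combination is described afterwards. Protocol 4.3 presents finding highly effective combinations as the main purpose of the platform, and 17.1 hopes for a benefit greater than that of either component. If the external tropifexor figure is chosen after the Cohort 1 data are seen, the choice can decide the label for a middling result.

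**Working it through.** The readable text gives no effect size, SD or power for an interaction, so there is no figure of the plan's own to reproduce. The question is what the two arms identify.

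**Step 1: what is estimable.** Write P, L, T and C for the geometric mean ratio to baseline under placebo, LYS006, tropifexor and the combination. On the log scale:

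- increment: log C − log L
- tropifexor effect: log T − log P
- interaction: (log C − log L) − (log T − log P)

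With only L and C observed, a matrix-rank check shows that C versus L is estimable. L versus P, T versus P, C versus T and the interaction are not. More participants would not change this. Even a tropifexor-alone arm would leave the interaction non-estimable without a placebo value.

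**Step 2: how far the label depends on the external value.** Back-transformed, interaction ratio = (C/L) / (T/P). For markers where a fall is benefit, below 1 is synergy and above 1 is antagonism. All effect sizes here are assumptions.

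| C/L (Cohort 1) | T/P = 0.80 | T/P = 0.70 | T/P = 0.60 |
|---|---|---|---|
| 0.50 | 0.625 | 0.714 | 0.833 |
| 0.70 | 0.875 | 1.00 | 1.167 |
| 0.80 | 1.00 | 1.143 | 1.333 |
| 1.00 | 1.25 | 1.429 | 1.667 |

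For example, 0.70/0.80 = 0.875, 0.70/0.70 = 1.00 and 0.70/0.60 = 1.167. Only the 0.70 row spans all three labels. At 0.50 every entry is synergy, at 1.00 every entry is antagonism, and at 0.80 there is no synergy.

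**Step 3: the placebo figure matters too.** If the external input is tropifexor's change from baseline rather than its effect versus placebo, a placebo value must also be chosen. Protocol Table 4-2 gives liver-fat changes on placebo of −3.0% and −9.6% in two 12-week studies. Assume LYS006 −15% and the combination −30%. The tropifexor-alone change at which the effects are exactly additive is then C × P / L − 1:

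- P = 0.970: 0.70 × 0.970 / 0.85 = 0.799, so −20.1%
- P = 0.904: 0.70 × 0.904 / 0.85 = 0.744, so −25.6%

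**Step 4: scale (secondary).** Protocol 12.5.1 and SAP 6.2.3 analyse ELF, ALT and % liver fat both as log ratio and as change from baseline. Suppose effects are exactly additive on the log scale, with no change on placebo. The interaction in absolute change is then baseline × LYS006 reduction × tropifexor reduction. With baseline liver fat 20% and tropifexor −30%, LYS006 at −10% gives 20 × 0.10 × 0.30 = +0.6 points, and at −30% gives 20 × 0.30 × 0.30 = +1.8 points. No precision attaches to these figures. They show only that the scale must be named.

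**The case against.** The strongest reply is that the reliance on outside data is deliberate. Protocol 4.3 limits single-drug arms to drugs not yet measured. Tropifexor has been measured against placebo over 12 weeks, so the design measures the unmeasured drug here and borrows the other. On that reading 17.1.1.3 merely says the arm supplies a missing piece, and its plural reference to single-agent effects presupposes that both are known. The study is non-confirmatory, and no readable objective, endpoint, sample size or decision rule concerns synergy. The scale worry is modest, because log ratio is listed first and is the only scale of the joint three-marker model.

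Most of this stands, and it is why the point is minor. It does not rescue the sentence. The historical-placebo comparison in 4.3 concerns the single-drug arm, so here it gives LYS006 versus placebo, not tropifexor versus placebo. The readable tropifexor data are preliminary, come from another study, do not mention ELF and show no effect size. A later tropifexor-alone cohort would not be randomised concurrently with Cohort 1, and Protocol 12.5.1 itself anticipates population drift.

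A reader might go further than the documents allow in three ways:

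- **That any Cohort 1 result would fit all three labels.** The table shows otherwise. If tropifexor's reported benefit on liver fat and ALT carries over, C/L of 1 or more on those markers points to antagonism whatever the size of that benefit.
- **That no external source has been planned.** Text is redacted directly after 17.1.1.3 and in the Arm 2 rationale, so this cannot be known.
- **That Arm 2 versus Arm 1 is not analysed.** Model text in Protocol 12.5.1 and SAP 6.2.3 is redacted, and both visibly plan a between-treatment comparison of % liver fat in a subgroup.

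**Conclusion.** The point holds, at minor severity. Cohort 1 identifies the incremental effect of adding tropifexor to LYS006 and nothing more between treatments. Any classification of the interaction needs a tropifexor-versus-placebo effect from outside the cohort, so it is a non-randomised, cross-study inference. That conclusion follows from the visible two-arm structure and needs no assumed numbers. Redacted text could name the external source but could not make it randomised.

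The size of the ambiguity does rest on assumptions. Over tropifexor-alone reductions of 20% to 40%, an intermediate result such as C/L = 0.70 can carry any of the three labels, while more extreme results cannot. The primary safety analysis is descriptive and unaffected.

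**What to change.** 1. In Protocol 17.1.1.3, restate the aim as estimating the incremental effect of adding tropifexor to LYS006.
2. Report Arm 2 minus Arm 1 with its 80% CI for ELF, ALT and % liver fat from the planned MMRM and ANCOVA models, if redacted text does not already provide it.
3. State that any conclusion on additivity, synergy or antagonism is an exploratory, non-randomised cross-study comparison on the log-ratio scale, using a tropifexor-versus-placebo source named in advance.

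The cost is a rewording in one cohort section and a sentence naming source and scale. The contrast comes from models already planned, and arms, sample size and visits stay as they are. The downside is that the stated aim becomes narrower.

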### **17.1.1.6 Drug-drug interaction**

Not applicable for this treatment arm.

### **17.1.1.7 Specific restrictions for study participants**

#### **17.1.1.7.1 Prohibited medications**

Use of the treatments displayed in [Table 17-3](#) is NOT allowed for this treatment arm for the duration of the prohibited period defined below.

**Table 17-3 Prohibited medications** Commercially Confidential Information

Medication		Prohibited period start	Prohibited period end
OAT3 inhibitors	CCI	Within 5 half-lives or 7 days of randomization, whichever is longer	End-of-study visit

#### **17.1.1.7.2 Dietary restrictions**

There are no specific dietary restrictions.

#### **17.1.1.7.3 Other restrictions**

Not applicable.

### **17.1.1.8 Specific safety stopping rules**

Not applicable.

Commercially Confidential Information

### **17.1.1.10 Specific study design considerations**

As this treatment does not have an extended half-life, the EOS1 visit will serve as the end-of-study visit for participants randomized to this treatment arm.

### **17.1.2 Cohort 1, Arm 2: LYS006 and tropifexor**

#### **17.1.2.1 Introduction**

This treatment arm will evaluate a free combination of LYS006 and tropifexor.

Commercially Confidential Information

Commercially Confidential Information

---

[figure not shown]
Commercially Confidential Information

#### 17.1.2.2.2 Tropifexor

Tropifexor, also known as LJN452, is a highly potent, specific and orally available non-bile acid agonist of the bile acid receptor FXR and is currently being evaluated in early phase healthy subject and patient studies.

#### 17.1.2.2.3 Background on FXR receptor

The bile acid receptor, farnesoid X receptor (FXR), is a nuclear receptor expressed in liver, intestine and kidney. FXR acts as a sensor of elevated bile acids and initiates homeostatic responses to control bile acid levels and modulate other metabolic processes such as gluconeogenesis and lipogenesis (Pattni et al 2012, Walters et al 2015). FXR agonism modulates bile acid synthesis and detoxifying metabolism. In the setting of NASH, as shown in [Figure 17-2](#) below, FXR agonism in both the liver and the gut has the potential to provide multimodal benefits which, in brief, include: reduction of fat accumulation in liver via decreased de novo lipogenesis, reduction of hepatic inflammation, anti-fibrotic effects mediated by stellate cells via decreased oxidative stress, and reduction of bacterial and lipopolysaccharide translocation from gut which induces inflammation (Schaap et al 2014).

**Figure 17-2 Potential efficacy of FXR agonism in NASH**

Adapted from [Schaap et al 2014](#).

Clinical validation of a FXR agonist for the treatment of NASH has been shown in clinical trials with obeticholic acid (OCA), a semi-synthetic variant of the natural bile acid chenodeoxycholic acid. In a small study in 20 patients with NAFLD and type 2 diabetes mellitus in which OCA was given for 6 weeks, OCA 25 mg improved insulin sensitivity and reduced circulating alanine aminotransferase (ALT) concentrations ([Mudaliar et al 2013](#)). In a larger trial (n=219), it was shown that 45% of NASH patients receiving 25 mg OCA QD for 72 weeks had improved liver histology compared to 23% of NASH patients receiving placebo in the same period ([Neuschwander-Tetri et al 2015](#)). Commercially Confidential Information

---

Commercially Confidential Information

#### 17.1.2.2.5 Tropifexor clinical data

Commercially Confidential Information

#### **Tropifexor human safety and tolerability**

Commercially Confidential Information

Currently participants are receiving monotherapy tropifexor in ongoing studies CLJN452X2201 (Primary Biliary Cholangitis [PBC]), CLJN452X2202 (primary Bile Acid Diarrhea [pBAD]) and CLJN452A2202 (non-alcoholic steatohepatitis [NASH]). Patients are also receiving tropifexor in combination with cenicriviroc in study CLJC242A2201J (NASH) at multiple sites across the world.

Commercially Confidential Information

Commercially Confidential Information

In summary, in clinical studies tropifexor has been well tolerated to date, with doses currently being tested up to 200 µg orally in the ongoing phase 2 NASH program.

Please see the tropifexor Investigator's Brochure for more information on other potential or hypothetical safety risks.

Commercially Confidential Information

### **Tropifexor human efficacy in NASH**

Preliminary data from the ongoing Novartis CLJN452A2202 study in patients with NASH provides evidence that tropifexor 90 µg daily for 12 weeks improved liver fat and ALT versus placebo. 140 µg and 200 µg daily doses of tropifexor are under evaluation in this study at the present time.

#### **17.1.2.2.6 Tropifexor dose rationale**

The current non-clinical safety profile of tropifexor (tropifexor IB), the DMC's recommendation based on first NASH clinical data and pharmacokinetic data, and clinical data in NASH patients to date from study CLJN452A2202, support evaluation of a tropifexor CCI in this study as outlined below.

Commercially Confidential Information

Commercially Confidential Information

Commercially Confidential Information

---

Commercially Confidential Information

Commercially Confidential Information

---

Commercially Confidential Information

### **17.1.2.7 Specific restrictions for study participants**

#### **17.1.2.7.1 Prohibited medications**

Use of the treatments displayed in [Table 17-7](#) is NOT allowed for this treatment arm for the duration of the prohibited period defined below:

**Table 17-7 Prohibited medications** Commercially Confidential Information

Medication		Prohibited period start	Prohibited period end
OAT3 inhibitors	CCI	Within 5 half-lives or 7 days of randomization, whichever is longer	End-of-study visit

#### **17.1.2.7.2 Dietary restrictions**

There are no specific dietary restrictions.

#### **17.1.2.7.3 Other restrictions**

Not applicable.

### **17.1.2.8 Specific safety stopping rules**

Not applicable.

Commercially Confidential Information

### **17.1.2.10 Specific study design considerations**

As these treatments do not have extended half-lives, the EOS1 visit will serve as the end-of-study visit for participants randomized to this treatment arm.

## 1 Introduction

### 1.1 Scope of document

The Reporting Analysis Plan (RAP) documents contain detailed information to aid the production of Statistics & Programming input into the Clinical Study Report (CSR) for trial “**CADPT02A12001**”.

The Statistical analysis plan (SAP) describes the implementation of the statistical analysis planned in the protocol.

Tables, Figures, Listings (TFL) detail the presentation of the data, including shells of summary tables, figures and listings, and Programming Datasets Specification (PDS) contains programming specifications e.g. for derived variables and derived datasets, to support the creation of CSR outputs.

### 1.2 Study reference documentation

Final study protocol, version v04, 02 Jun 2021 and final SOM, version v02, 17 Aug 2021 are available at the time of finalization of Statistical Analysis Plan.

### 1.3 Study objectives and related endpoints

#### 1.3.1 Primary objective(s) and related endpoints

Primary objective	Endpoints related to primary objective
To determine the safety and tolerability of single or combination therapy during 12 weeks of treatment.	Safety endpoints (including vital signs, physical examination, laboratory measurements, ECG); Adverse events.

#### 1.3.2 Secondary objective(s) and related endpoints

Secondary objective(s)	Endpoints related to secondary objectives
To determine the effect of single or combination therapy on circulating markers of ongoing liver fibrosis	Enhanced Liver Fibrosis (ELF) Test
To determine the effect of single or combination therapy on intrahepatic lipid content	Percent (%) liver fat as measured by Magnetic Resonance Imaging-Proton Density Fat Fraction (MRI-PDFF)
To determine the effect of single or combination therapy on cardiometabolic risk parameters	Body weight, waist and hip circumference, waist-to-hip ratio, Homeostasis Model Assessment of Insulin Resistance (HOMA-IR), hemoglobin A1c (HbA1c), fasting glucose, fasting insulin, fasting lipid profile
To determine the effect of single or combination therapy on circulating markers of liver and/or systemic inflammation	Liver function test (ALT), high-sensitivity C reactive Protein (hsCRP)

To evaluate the pharmacokinetics (PK) of each individual agent when administered as a single or combination therapy.	Plasma concentrations
--	-----------------------

Commercially Confidential Information

#### **1.4 Study design and treatment**

This is a non-confirmatory, multicenter, open label, platform study in NAFLD patients with a NASH-like biomarker phenotype to examine the effects of single and combination therapies over 12 weeks of treatment.

[figure not shown]
Commercially Confidential Information

Commercially Confidential Information

There is a maximum of five cohorts planned. Each cohort will consist of a 33-day screening period (Day -60 to Day -28), a baseline period of 27 days (Day -27 to Day -1), a treatment period of 12 weeks (Day 1 to Day 85), and a study completion evaluation (End of Study [EOS] 1) approximately 28 days after the last drug administration (Day 113). CCI

Participants will be advised to maintain their recommended diet for NAFLD during the study. The study design scheme is shown below in [Figure 1-1](#):

**Figure 1-1 Study design**

## 2 First interpretable results (FIR)

First interpretable results (FIR) will be provided for this trial at each IA and at the end of study (CSR).

The study FIR template (mock slides) can be found in CREDI in the study RAP folder.

The template shows the analysis / results to be presented in the FIR. Study outputs required to be created at the time of the FIR will be highlighted in TFL shells document and marked as "Key" in the Programming Deliverables Tracker (PDT) output list.

## 3 Interim analyses

Commercially Confidential Information

Commercially Confidential Information

